6. ASSESSMENTS

At predefined time points, all participating patients will undergo a series of assessments in order to evaluate the safety and tolerability of AG019 alone as well as the safety and tolerability of AG019 co-administered with teplizumab. Additional assessments will be done in order to evaluate the pharmacodynamics activity and the pharmacokinetic profile of AG019 alone as well as the safety and tolerability of AG019 co-administered with teplizumab.

XXX

6.1.General assessments

General assessments for this study will include:

- Informed Consent: Before study procedures are performed, patients will be informed about
 the study and required to sign and date the IRB/IEC approved ICF. For patients <18 years of
 age, assent of the patient will be obtained, as well as consent from the parents and/or legally
 acceptable representative. Details about informed consent procedure are listed in Section
 11.3.
- Inclusion/exclusion criteria: As part of the screening visit, all inclusion and exclusion criteria listed in Section 4 will be verified.
- Medical History and demographic data:
 - the medical history comprises a general medical history (including history of alcohol abuse, illicit drug abuse and smoking history), relevant T1D related medical history (including date of diabetes diagnosis, relevant glycaemia levels, autoantibody positivity, current insulin use and start date of insulin therapy as applicable) and medication history
 - Demographic data will include age, ethnicity and year of birth
- Physical examination including visual inspection of skin, examination of eyes, ears and throat, auscultation of heart, lungs and abdomen, and percussion/palpation of abdomen. Other assessments may be performed at the discretion of the investigator. Clinically significant abnormalities will be recorded in the eCRF.
- **Vital signs** including height (collected at screening only), weight, sitting blood pressure, heart rate, respiratory rate and body temperature.

Confidentiality Statement

- 12-lead electrocardiogram (ECG): To monitor the heart function of the study participants, the investigator will perform a 12-lead ECG and will determine whether the result of this test is normal or not. Abnormal test results will be recorded as adverse events.
- Placement of a continuous glucose monitoring (CGM) device: Once all in/exclusion criteria
 are verified, the investigator will train the patient on the placement of the CGM device during
 the baseline visit. The CGM device will be placed, so the patient will know how to do this at
 home. The placement of the CGM, as well as the first CGM reading, will be done prior to
 administration of the first dose of study drug(s). The Sponsor will supply the CGM devices.
- **Tuberculosis test:** As part of the eligibility verification, all patients will undergo a test to determine whether the patient shows signs of active or latent tuberculosis. The decision on the type of test to be used is left to the discretion of the investigator, and could include e.g. TST, TSPOT, QuantiFeron or other appropriate tests.
- Concomitant medications: At every visit, the investigator will obtain information about concomitant medications the patient is taking (including dose, frequency, route of administration, start and stop dates)

6.2.Safety Assessments

Safety will be assessed by collecting and recording Adverse Events (AEs) and laboratory assessments and the presence of *L. lactis* sAGX0407 in whole blood.

The study will utilize local laboratories for safety assessments. The clinical laboratory will indicate laboratory values out of normal ranges. The Investigator must assess all abnormal clinical laboratory results for clinical significance in a timely fashion. A notation of 'clinically significant' (CS) or 'non-clinically significant' (NCS) with initials and date will be documented on the respective laboratory report next to any abnormal value. An abnormal clinical laboratory value will be considered and documented as an AE, if in the opinion of the Investigator, it is clinically significant. The Investigator will follow proper adverse event reporting procedures.

For details on the data to be collected for adverse events, please refer to Section 8.

XXX

6.3.Laboratory Assessments

6.3.1General considerations

Throughout the study, blood samples will be collected at regular intervals, as described in the Visit schedule

XXX

Confidentiality Statement

XXX

6.3.2Local lab assessments

Parameters to be analysed will include:

- Hematology: complete blood count: Red Blood Cell (RBC) count, haemoglobin, haematocrit, mean corpuscular volume (MCV), mean corpuscular haemoglobin (MCH), mean corpuscular haemoglobin concentration (MCHC), RBC distribution width (RDW), white blood cell (WBC) count, differential count, platelet count
- Serum Chemistry: blood glucose, sodium, potassium, chloride, calcium, CO₂/bicarbonate
- Liver function tests: alkaline phosphatase (ALP), AST, ALT, lactate dehydrogenase (LDH), total protein, albumin, total bilirubin
- Pregnancy tests for women of childbearing potential: serum (at screening), urine (at other visits the Sponsor can provide urine dip sticks if needed)
- Coagulation tests: INR
- Inflammatory: C-reactive protein (CRP)

Following additional blood parameters will be analysed at screening, and if no concerns are identified, these parameters will not require analysis at follow-up visits:

- Kidney function tests: uric acid, urea/blood urea nitrogen (BUN), creatinine, estimated glomerular filtration rate (eGFR)
- Cardiovascular tests: total cholesterol, triglycerides, high density lipoproteins (HDL), low density lipoproteins (LDL), very low density lipoproteins (VLDL - optional)
- Thyroid stimulating hormone (TSH)

Total bilirubin, AST, ALT, LDH, Complete Blood Count (CBC), and INR will be evaluated to verify the need to withhold teplizumab (or placebo) infusion before each (potential) teplizumab administration, as described in the Visit Schedule The drug infusion withholding criteria presented in Section 11.4.3.5 should be evaluated.

In addition to the above lab assessments to be analysed by the site's local lab, EBV/CMV/HCV/HBV/HIV monitoring assessments will be done. Potential reactivation will be assessed at regular intervals by viral serologies (IgG/IgM) and/or polymerase chain reaction (PCR) for viral load.

As part of the eligibility verification, the presence of one or more autoantibodies against beta cell antigens will be verified. If documentation of autoantibody positivity is found in the patient's medical file, the assessment does not have to be repeated at screening.

As part of the eligibility verification, all new patients will be tested for SARS-Cov2 at screening and within 3 days before the start of teplizumab/placebo infusions.

Confidentiality Statement

6.3.3Central lab assessments

6.3.3.1Pharmacokinetic Assessments

Following parameters will be assessed for analysis of systemic and local exposure to *L. lactis*:

- Presence of live L. lactis clinical strain bacteria in whole blood,XXX
- Measurable serum levels of hIL-10 and hPINS, XXX
- Presence of L. lactis clinical strain bacteria in fecal excretion, XXX

Throughout the study, blood and feces samples will be collected at regular intervals for analysis by the central laboratory, as described in the Visit schedule.

- Blood sample collection for PK analysis, collected form all repeat dose patients in all AG019 cohorts and the combination cohorts
- Feces sample collection for PK analysis, collected from all repeat dose patients in AG019 Cohorts 2 and 4, and from all patients in the combination cohorts

Blood and feces samples for PK assessments will be analyzed by a central lab.

Details on sample collection, labeling, storage, shipment and analysis are described in the central lab manual.

The Site will train the patients on how to collect feces samples. All stool samples will be collected and labeled with patient number, and date and time of sample collection.

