6.4.1 Electronic Patient Reported Outcomes (ePRO)

All patients (except for the single dose patients) will be asked to keep an electronic diary. The diaries will contain following information:

Confidentiality Statement

- Safety related information (all experienced adverse events and serious adverse events, including signs of clinical sepsis and known risks associated with the use of anti-CD3 mAb or with T1D glycemic control)
- Occurrence of hypoglycemic events including all relevant information for standard classification (these will be captured separately from other safety related information)
- Deviations from planned study drug intake (e.g. missed doses or incorrect doses taken)
- Changes in concomitant medication intake
- Insulin requirements: Daily

The electronic diaries will be kept from the day of signing the informed consent until the patient is withdrawn or completes the study.

A site research coordinator will train the patients on how to complete the electronic diary.

The research coordinator will review these diaries at every follow-up visit to verify that they have been completed properly and consistently. If needed, the patients will be re-trained on the completion of the diary. All relevant data reported in the diaries will be translated into the eCRF by the research coordinator.

6.4.2Continuous Glucose Monitoring (CGM)

All study patients (except for the single dose patients) will receive a XXX CGM device for the entire duration of their study participation. The investigator will train the patients on how to place the CGM device and will provide written instructions to the patient. The data generated by the device will be downloaded at every site visit. The devices will store data for up to 30 days.

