7.3. Repeat Dose Patients

7.3.1Screening Visit (Day -28 – Day 0)

Following screening observations and procedures will be completed within 28 days prior to randomization:

- Signed and dated ICF
- Assessment against inclusion and exclusion criteria
- Medical history
- Demographic Data
- Physical Exam
- Vital signs
- 12-lead ECG
- Serum pregnancy test (in females of childbearing potential)
- Blood sampling for local lab (hematology, full chemistry, specific screening blood analysis, infectious disease, autoantibodies)
- SARS-Cov2 PCR test (only applicable for patients in the combination cohorts)
- Blood sampling for mechanistic assessments (only for repeat dose patients in AG019 Cohorts
 2 and 4 and for patients in the combination cohorts)
- Blood sampling for central lab (HbA1c)
- Blood sample for central lab PK
- Feces collection for central lab PK¹⁰ (only for repeat dose patients in AG019 Cohorts 2 and 4 and for patients in the combination cohorts)
- Tuberculosis test
- Mixed Meal Tolerance Test (MMTT) for C-peptide and glucose assessments
- Drugs of abuse test
- Record concomitant medications
- Record adverse events
- ePRO preparation / explanation
- Assessment of insulin use and hypoglycemic events
- Register patient in IRT
 - Registration in IRT should be done as soon as eligibility is confirmed and ICF is signed to allow for timely shipment of study drug. Ideally this should be done at least 1 week before the Day 1 visit (start of treatment visit).

7.3.2Baseline Visit (Day 1 – start of active treatment)

Prior to the first administration of IMP, following observations and procedures will be completed:

Confidentiality Statement

This document contains confidential information. It is intended solely for the use of the principal investigator, coinvestigators, staff, appropriate institutional review boards or ethical committees, and other required regulatory bodies.

AG019-T1D-101 CSP Final 9.0 11-Jun-2020

¹⁰ Sites should make every reasonable effort to collect feces during the screening visit. If feces cannot be collected during the screening visit, patients will be asked to collect feces between the Screening visit and the Day 1 visit, according to the instructions provided by the site and the collection materials provided by the central lab.

- SARS-Cov2 PCR test (only applicable for patients in the combination cohorts, to be taken within
 3 days before the first teplizumab/placebo infusion)
- Register visit in IRT
- Physical Exam
- Vital Signs

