- Urine pregnancy test (in women of childbearing potential)
- Blood sampling for mechanistic assessments (only for repeat dose patients in AG019 Cohorts
 2 and 4 and for patients in the combination cohorts)
- Record concomitant medications
- Record adverse events
- Placement of CGM device, training of patient on how to place the CGM device at home
- ePRO review including insulin use and hypoglycemic events
- Blood sampling for local lab (hematology, full chemistry, INR)
- Evaluation of drug infusion withholding criteria (only for Combination Cohorts)
- Administer first dose of AG019/placebo (for combination cohorts, randomized treatment should be respected)
- First teplizumab/placebo (randomized treatment should be respected)

For patients enrolled in the Repeat Dose AG019 cohorts, it is recommended to schedule the Day 1 visit on a Friday, to avoid having to schedule follow-up visits on weekend days.

For patients enrolled in the Combination cohorts, it is recommended to schedule the Day 1 visit on a Monday, to avoid study drug infusions in 2 consecutive weekends.

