In addition to the above lab assessments to be analysed by the site's local lab, EBV/CMV/HCV/HBV/HIV monitoring assessments will be done. These measurements were performed at screening for all patients and at Visit 13-16, Visit 19 for repeat dose patients. Potential reactivation will be assessed at regular intervals by polymerase chain reaction (PCR) for viral load.

For hematology, clinical chemistry, liver function, coagulation parameters and CRP summary statistics will be produced for observed values. In addition, the difference from baseline to each visit at which they were assessed will be derived and presented.

Shift tables showing the number of subjects who changed from normal, abnormal not clinical significant or abnormal clinical significant at baseline to normal, abnormal not clinical significant or abnormal clinical significant at each post-baseline time of assessment will be presented.

Figures showing mean and median values over time per cohort will be shown for CRP, AST and lymphocytes.

Number of patients with positive/negative serology at baseline and positive/negative for PCR per visit will be tabulated.

All laboratory parameters will be listed. Abnormal values will be flagged in listings.

In addition, all study patients (except for the single dose patients) will receive a XXX continuous glucose monitor (CGM) device for the entire duration of their study participation. The data generated by the device will be downloaded at every site visit. The devices will store data for up to 30 days. The device measures glucose every 5 minutes, thus every measurement will be said to have a duration of 5 minutes when the calculation of total duration is performed. The first measurement is said to measure the glucose value 5 minutes before the actual measurement. For the CGM data collected at each visit:

- The total CGM recording time,
- Time in range (the time greater than or equal to 71 mg/dl and less than or equal to 179 mg/dl),
- Time above range (the time above 179 mg/dl),
- Time in the low range (the time below 71 mg/dl),
- Time in the very low range (the time below 50 mg/dl) and
- Time with missing values

will be summarized in hours/minutes and percentages of the total CGM recording time, per cohort.

Physical Examination

The physical examination included visual inspection of skin, examination of eyes, ears and throat, auscultation of heart, lungs and abdomen, and percussion/palpation of abdomen. The results will be recorded as

- Normal,

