- Abnormal Not Clinically Significant or
- Abnormal Clinically Significant.

For repeat dose patients the physical examination will be performed at Visit 1, 2, 5, 8, 13-19. For single dose patients the physical examination will be performed at screening, treatment and post treatment.

The frequencies (and percentage) of normal, abnormal but not clinically significant or abnormal and clinically significant will be tabulated.

Physical Examination data will be listed.

ECG

The investigator will perform a 12-lead ECG. The results will be recorded as

- Normal,
- Abnormal Not Clinically Significant or
- Abnormal Clinically Significant.

For single dose patients ECG status will be collected at screening (Visit 1) and at post treatment only if there is a suspicion of cardiac problems. For repeat dose patients ECG status will be collected at Visit 1, Visit 15, Visit 19 and in addition at Visit 17 if there is a suspicion of cardiac problems.

The frequencies (and percentage) of normal, abnormal but not clinically significant or abnormal and clinically significant will be tabulated.

ECG data will be listed.

Hypoglycemic events

Hypoglycemic events will be documented in the patient diary. Events of hypoglycemia will be classified as outlined below.

- hypoglycemia Level 1: A glucose alert value of 3.9 mmol/l (70 mg/dl) or less for at least 20 minutes
- hypoglycemia Level 2: A glucose level of <3.0 mmol/l (<54 mg/dl), sufficiently low to indicate serious, clinically important hypoglycemia.
- hypoglycemia Level 3: Severe hypoglycemia, as defined by the American Diabetes Association, denoting severe cognitive impairment requiring external assistance for recovery.

For the purposes of this study, hypoglycemia events classified as level 1 will not be recorded separately on the hypoglycemia event electronic case report form (eCRF), unless the investigator feels that the event is medically important. Hypoglycemia events level 2 and 3 will be recorded separately on the hypoglycemia event eCRF. The evaluation that produced the value or result should be repeated until that value or result returns to normal or can be explained and the participant's safety is not at risk. In addition, all hypoglycemia events meeting the definition of SAE should be recorded as serious adverse events in the eCRF.

Time of the events will be divided in the following time periods:

- Pre-treatment: all events until the day before treatment start

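### The study CGM starts on the day that divides pre-treatment from on-treatment hypoglycaemia counts, so the two columns are not comparable and the CGM table has no pre-dose value

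*Protocol*

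**What the plan says.** **Sensor.** Protocol 6.1 has the patient trained and the sensor fitted at the baseline visit, after eligibility has been verified: "The placement of the CGM, as well as the first CGM reading, will be done prior to" the first dose. The visit list agrees. Under "7.3.2Baseline Visit (Day 1 – start of active treatment)" it has the item "Placement of CGM device, training of patient on how to place the CGM device at home". The screening list in 7.3.1 has no CGM item. Protocol 6.4.2, repeated in SAP 6.3.9, nonetheless gives every patient except the single-dose patients a "CGM device for the entire duration of their study participation". SAP 6.3.9 adds: "The device measures glucose every 5 minutes".

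**Diary.** Protocol 6.4.1 states: "The electronic diaries will be kept from the day of signing the informed consent until the patient is withdrawn or completes the study". Diary training ("ePRO preparation / explanation") and an assessment of hypoglycaemic events are both on the screening list.

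**Table.** SAP 6.3.9 has hypoglycaemic events documented in the diary and divides time into three periods. The first is "Pre-treatment: all events until the day before treatment start". The second runs from Day 1 to the last treatment day, and the third covers everything after that. Numbers of events and of patients with events are tabulated by cohort, treatment, level and period. SAP 6.3.9 summarises CGM data separately, as time in, above and below range.

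**The concern.** The start of the sensor and the boundary between the first two columns fall on the same day. Before Day 1 a low glucose value can come to light through symptoms or a home meter, which Protocol 6.3.3 mentions in its mixed-meal test instructions. From Day 1 the patient also wears a sensor that reads every 5 minutes. Level 2 is defined by a glucose value alone, so how many such events are found can depend on how often glucose is measured. The SAP does not say which glucose source qualifies an event, does not adjust for period length, and carries no caveat about Day 1.

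Hypoglycaemic events are a named secondary safety endpoint (SAP 3.2). Phase 1b has no control arm, and the combination cohorts have very few placebo patients. A reader will therefore tend to use the pre-treatment column as the reference. A difference between columns could then be credited to AG019 or teplizumab, or could hide an effect, when part of it comes from measurement.

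**Working it through.** The plan states no figure on this point, so there is none to reproduce. The check compares dates and exposure.

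**Inputs.** Screening window up to 28 days (Protocol 4). Treatment 56 days (Protocol 5.1.1). Last visit Day 360 (Protocol 7.3.4.4). One sensor reading per 5 minutes (SAP 6.3.9). Randomisation of 10 patients per combination cohort at 4:1 (Protocol 5.9).

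**1. Sensor coverage by SAP period.** The pre-treatment period ends the day before Day 1 and the sensor is fitted on Day 1.
- Pre-treatment: 0 of up to 28 days.
- During treatment: up to 56 days, at 24 × 60 / 5 = 288 readings a day, so 288 × 56 = 16,128 per patient if none are missing.
- The pre-dose reading on Day 1 counts as during treatment, because the SAP puts all of Day 1 there.
- The first CGM download on the visit lists is at Day 4, so the CGM table has no pre-dose row.

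**2. Period length.** Up to 28 days before, 56 during, and 360 − 56 = 304 after treatment. With a constant event rate and unchanged detection, the expected on-treatment to pre-treatment count ratio is 56 / 28 = 2.0. If only 14 of the 28 screening days are used it is 56 / 14 = 4.0. The after to before ratio is 304 / 28 = 10.9. These ratios need no assumption about the sensor.

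**3. Detection, as illustration only.** Let s be the number of recordable events found without the study sensor, divided by the number found with it. With no true change in rate, the apparent rate ratio (on / pre) is 1/s and the raw count ratio with a 28-day pre-period is 56 / (28 × s) = 2/s. The documents give no value for s, so the range below is an assumption.

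| s (assumed) | Rate ratio 1/s | Count ratio 2/s |
|---|---|---|
| 1.00 | 1.00 | 2.00 |
| 0.75 | 1.33 | 2.67 |
| 0.50 | 2.00 | 4.00 |
| 0.25 | 4.00 | 8.00 |

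**4. Which levels are exposed.** Protocol 8.4 sends Levels 2 and 3 to the hypoglycaemia eCRF, and Level 1 only if the investigator thinks it medically important. Level 3 requires outside assistance and would come to light without a sensor. Level 2 is the exposed category.

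**5. Concurrent reference.** Placebo patients per combination cohort: 10 × 1/5 = 2, so 4 in all. Phase 1b: none.

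**The case against.** **The recording route does not change.** This is correct. The diary and eCRF are used in every period, and no text says that sensor readings create hypoglycaemia records. The link from sensor to diary is an inference. It has some support: Level 1 and the non-major hyperglycaemia definition (Protocol 8.4) both need a 20-minute duration, and Protocol 5.1.4 warns that paracetamol can cause false high-glucose signals on the CGM. That makes the link probable, not established.

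**Direction and size are unknown.** Also correct. A reader might infer that on-treatment counts will be inflated by a known factor. The documents do not support that. The device is redacted, and the text does not say whether patients see live readings. If readings are masked, most of the mechanism disappears. If they are visible, patients may avert lows and the true rate could fall. Patients already using their own CGM would change little, and their number is not given.

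**The pre-treatment period is not the only within-patient reference.** A reader might take it to be so. The post-treatment period keeps the same sensor and diary for about 304 days. It is not a clean baseline, since it follows treatment and the device stores only 30 days of data between widely spaced downloads, but it exists.

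**The study is descriptive.** No test, no rate ratio and no formal comparison of periods is planned. SAP 6.5 says generally that summary tables show changes from baseline, but SAP 6.3.9 plans none for CGM. This limits the consequence. It does not make the columns comparable.

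**Moving placement to screening would conflict with the protocol.** Protocol 6.1 puts training after eligibility is confirmed, so placement at the screening visit itself would not fit. The SAP also describes enrolment in the past tense (4.1) and reports two interim analyses as done (6.9), so a change in placement may now reach few or no patients.

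**Conclusion.** The point holds as one of comparability. Study CGM covers no part of the pre-treatment period, although the text describes coverage of the whole participation. The hypoglycaemia table divides time on the day the sensor starts. Unequal period lengths alone make raw counts unsuitable for comparing before with during treatment: the ratio is at least 2 to 1 under a constant rate for a patient who completes 56 days. A change in detection of Level 2 events on Day 1 is probable and would add to this or offset it by an unknown amount. The 1.33 to 4.0 range of rate ratios only shows what the assumed values of s imply.

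The effect is confined to the hypoglycaemia and CGM summaries. It matters most in the four Phase 1b cohorts and next in the combination cohorts with 2 placebo patients each. A reader might extend it to the primary endpoint or to glycaemic safety as a whole. The documents do not support that: TEAE incidence is not directly affected, and HbA1c and insulin use keep their own baseline values. It is a low-cost improvement, not a fault in the primary analysis.

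**What to change.** **(a) Any patient not yet dosed.** Train the patient and fit the CGM as soon as eligibility is confirmed, at about the time of IRT registration, instead of on Day 1. Protocol 7.3.1 already prefers registration a week or more ahead of Day 1, which would usually give several days of sensor data without promising a fixed number. Show these data as the baseline row of the SAP CGM table. Cost: earlier wear, some devices used by patients who are never dosed, and possibly one earlier training contact. The sponsor already supplies the devices.

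**(b) Patients without pre-dose CGM.** Mark the pre-treatment column of the hypoglycaemia table *diary/meter only, not comparable*, or drop it. In every period report events per patient-time beside the counts. Cost: SAP wording and a denominator from dates already collected. This part remains possible if enrolment is complete.

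**(c) Wording.** Reconcile the coverage statement in Protocol 6.4.2 and SAP 6.3.9 with placement on Day 1. Cost: an editorial change.

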⁷ Age-dependent enrolment in each cohort needs to be considered when evaluating this inclusion criterion.

Confidentiality Statement

This document contains confidential information. It is intended solely for the use of the principal investigator, coinvestigators, staff, appropriate institutional review boards or ethical committees, and other required regulatory bodies.

AG019-T1D-101 CSP Final 9.0 11-Jun-2020

Inclusion Criteria	AC	СС
Ability and willingness of patient to participate fully in all aspects of this clinical study	Х	Х
Written informed consent obtained and documented (patient, parent, guardian as applicable)	Х	Х
Willingness to use a continuous glucose monitoring device and willingness to comply with the protocol defined glucose monitoring (note: this inclusion criterion does not apply to single dose patients)	Х	х
 Total bilirubin ≤1.0 x upper limit of normal (ULN) Aspartate aminotransferase (AST) or alanine aminotransferase (ALT) ≤1.5 x ULN ≥1,000 lymphocytes/μL ≥1,000 polymorphonuclear neutrophils (PMN)/μL ≥100,000 platelets/μL Hgb ≥10 g/dL Serum Creatinin ≤1.5 x ULN eGFR ≥60 mL/min/1.73m² INR ≤0.1 above upper limit of normal Absence of clinically significant age appropriate abnormalities on all other lab values, except for abnormalities directly attributable to T1D. 	Х	Х

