Prohibited therapy during the entire treatment period includes any antibiotic treatment known to affect the viability of L. lactis sAGX0407 (see Appendix B), β -cell stimulants, immunosuppressive or immunomodulatory therapies, including systemic steroids, other investigational drug(s), vaccination with live virus or organism, anti-CD3 antibody, any anti-diabetic agents other than insulin, medications known to influence glucose tolerance and daily use of non-steroidal anti-inflammatory agents.

For patients enrolled in the combination cohorts, premedication with ibuprofen or similar non-steroidal anti-inflammatory drugs (NSAID) and with an antihistamine is recommended and may be useful in patients who develop rashes during teplizumab administration.

As paracetamol may induce false positive signals of hyperglycemia by the continuous glucose monitoring devices, its use for reasons other than the reasons mentioned in the previous paragraph should be avoided as much as possible throughout the study.

Confidentiality Statement

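### In the visible text, no kidney test after dosing is required unless screening raised an undefined concern, so renal worsening on treatment would not be routinely measured or summarised

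*Protocol*

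**What the plan says.** Protocol 6.3.2 splits the local laboratory tests into two lists. The first holds hematology, serum chemistry, liver function, pregnancy tests, INR and CRP. Its chemistry line is "Serum Chemistry: blood glucose, sodium, potassium, chloride, calcium", followed by CO2/bicarbonate. The second list is introduced by "Following additional blood parameters will be analysed at screening, and if no concerns are identified, these parameters will not require analysis at follow-up visits". It holds the kidney tests (uric acid, urea/BUN, creatinine, eGFR), lipids and TSH. SAP 6.3.9 carries the same two lists and the same rule.

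Entry limits are in Protocol 4.2: "Serum Creatinin ≤1.5 x ULN", "eGFR ≥60 mL/min" per 1.73 m², and, for the remaining tests, "Absence of clinically significant age appropriate abnormalities on all other lab values, except for abnormalities directly attributable to T1D".

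For repeat-dose patients, screening (7.3.1) names 'full chemistry' and, as a separate item, 'specific screening blood analysis'. Days 1, 4, 7 and 12 name 'full chemistry'. Days 28 to 360 and unscheduled visits name 'chemistry'. The labs that decide whether an infusion is withheld (5.5, 6.3.2, 11.4.3.5) are total bilirubin, AST, ALT, LDH, CBC and INR.

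On analysis, SAP 6.3.9 states: "For hematology, clinical chemistry, liver function, coagulation parameters and CRP summary statistics will be produced for observed values". Changes from baseline and shift tables follow. SAP 7.1 lists the same groups, plus HbA1c.

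**The concern.** The rule ties repeat testing to a pre-dose finding. That suits a test whose only purpose is eligibility, but not one meant to detect a treatment effect, because harm on treatment shows itself only after dosing. Any patients who were followed would be selected on their screening value, so their results would not describe the cohort.

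Safety and tolerability is the primary objective, and Protocol 4.6 describes the study as first-in-human. Under Protocol 6.2 an abnormal laboratory value becomes an adverse event only once the investigator has seen it and judged it clinically significant. A creatinine rise without symptoms that nobody measures therefore cannot enter the primary TEAE endpoint or reach the medical monitor or the DSMB. Protocol 10.7 also promises cross-tabulations of baseline against worst post-treatment abnormality for selected laboratory tests. These cannot be built for creatinine without post-dose values.

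**Working it through.** No stated figure in the plan bears on this, so the check is mainly one of text, followed by a count.

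**Step 1: can another panel bring the kidney tests back after dosing?**

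| Source of post-dose results | Content named | Renal marker named |
|---|---|---|
| Repeated serum chemistry (Protocol 6.3.2) | glucose, sodium, potassium, chloride, calcium, CO2/bicarbonate | none |
| Labs before each infusion (11.4.3.5) | total bilirubin, AST, ALT, LDH, CBC, INR | none |
| Days 4, 7, 12 (7.3.3.1) | hematology, 'full chemistry', INR | term undefined |
| Days 28 to 360 (7.3.3.1, 7.3.4) | hematology, 'chemistry' | none |
| Unscheduled visits (7.4) | hematology, 'chemistry', viral PCR | none |

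Only 'full chemistry' leaves room. At repeat-dose screening it stands beside 'specific screening blood analysis' as a separate item, and no later visit lists the latter. This suggests, without proving, that the kidney tests lie outside 'full chemistry'. For single-dose patients, the Day 4 draw (7.2.3) does not say what is analysed.

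**Step 2: can the trigger fire?** Creatinine above ULN up to 1.5 x ULN, and eGFR from 60 upward, are admissible. The broader clause on clinically significant abnormalities covers the other laboratory values, not these two, and exempts abnormalities attributable to T1D. An enrolled patient could therefore raise a concern at screening, depending on how the investigator reads that word. A patient with normal screening cannot, whatever happens on treatment.

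**Step 3: how many patients and draws?**

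- Repeat-dose patients: 4 AG019 cohorts x up to 6, plus 2 combination cohorts x 12 = 24 + 24 = up to 48.
- Active combination patients: 2 x (2 open-label + 8 of the 10 randomized 4:1) = 20. Placebo: 2 x 2 = 4.
- Visits after Day 1 with local chemistry: Days 4, 7, 12, 28, 56, 90, 180, 270, 360 = 9.
- Combination patients also have safety labs on Days 2, 3, 5, 6, 8, 9, 10, 11, so 9 + 8 = 17 post-dose draws.

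**Step 4: what would the added test show?** The documents give no renal event rate, so the rates p below are assumptions. For n = 20 active combination patients, all measured, with the event visible on a sampled day, the chance of at least one event is 1 − (1 − p)^20:

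| Assumed p | Chance of at least one event in 20 |
|---|---|
| 2% | 33% |
| 5% | 64% |
| 10% | 88% |
| 20% | 99% |

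If none were seen, the one-sided 95% upper bound is 1 − 0.05^(1/20) = 13.9%. For the 10 active patients of one cohort it is 1 − 0.05^(1/10) = 25.9%.

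**The case against.** The strongest reply is that the visible text does not prove an absence. The rule says repeat analysis is not required, which permits it. 'Full chemistry' might include creatinine. Appendix A, which governs the schedule, is not available, and text on laboratory assessments, infusion withholding and evaluation after withholding is blacked out. This stands. A reader might infer that no post-dose creatinine is planned at all, or that eligibility makes a concern impossible. The documents support neither.

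A reader might also infer that the trial could say nothing about renal safety. That goes too far. Clinically apparent renal events would be reported as TEAEs. Potassium, bicarbonate, weight and blood pressure are followed. The DSMB may ask for more information, and the SAP lists all laboratory parameters and flags abnormal values, so any renal value obtained would be seen. None of these is a reliable substitute for routine creatinine when the rise is silent.

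It can be said that the SAP merely follows the protocol, and that 4 placebo patients allow no useful comparison. Both are fair. The SAP change is a consequence of the protocol change, and the gain is descriptive, as is everything else in this study.

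Finally, a reader might build a renal argument on NSAID exposure. The visible text names no renal signal, and the recommendation covers only the combination cohorts. What the documents do show is that Protocol 5.1.4 states "premedication with ibuprofen or similar non-steroidal anti-inflammatory drugs (NSAID) and with an antihistamine is recommended" for those cohorts while listing daily NSAID use as prohibited during the treatment period. Those two statements must be reconciled.

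**Conclusion.** The point holds in a limited form. For a patient whose screening raised no concern, the visible text requires no creatinine, eGFR or urea/BUN after dosing, and the SAP names no kidney group in its summaries or shift tables. The SAP's 'clinical chemistry' is not defined, but its parameter list keeps kidney tests apart from serum chemistry. A silent decline in kidney function on treatment would therefore not be routinely detected or summarised. This applies to up to 48 repeat-dose patients, at 9 chemistry visits each after Day 1, and includes the 20 on active combination treatment.

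The conclusion rests on reading 'full chemistry' as excluding the kidney tests, and on Appendix A not adding them. If either is wrong, what remains is to define the term and add the SAP summary. This is an inexpensive improvement to the safety assessment. It contradicts no stated figure or endpoint and does not invalidate the plan.

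**What to change.** In Protocol 6.3.2, move creatinine (with eGFR) and urea/BUN from the screening-only list to the repeated serum chemistry panel, analysed on samples already drawn, for example at Days 12, 28 and 56. Define 'full chemistry' and align Appendix A with it. If any test stays conditional, define what counts as a concern. Lipids and TSH can stay screening-only.

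In SAP 6.3.9 and 7.1, add kidney function to the by-visit summaries with change from baseline and to the shift tables. The screening value already serves as baseline under SAP 6.3.1.

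In Protocol 5.1.4, reconcile the two NSAID statements.

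The cost is two or three analytes on existing tubes. At three visits this means at most 48 x 3 = 144 additional creatinine results, with a few more out-of-range values for investigators to review, and additional SAP output for one more laboratory group. No extra visit or blood draw is needed.
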